14. Whole blood for soluble markers from plasma, serum, and/or cellular markers. Blood samples will be collected on Day 1: pre-dose and at 1 hour (\pm 15-minute window), 6 hours (\pm 1-hour window), and 24 hours (Day 2 [\pm 8-hr window]) after the end of infusion. If a subject's duration of infusion is 3 hours or longer the 6 hour time point is optional. A pre-dose blood sample should be collected on Day 8, Day 15 and Day 29 for all cohorts. An additional sample will be collected at progression.
15. The study treatment dosing window is \pm 3 days for subjects on an every 2 week dosing schedule. If dosing does not occur on the intended day, all other assessments/subsequent visits should be changed accordingly relative to when the dose was received. Subsequent cohorts may receive different dosing schedules. Use the appropriate Time and Events Table as applicable.
16. An immunogenicity sample will be collected at the Follow-up and Post-study visits.
17. It is preferred that the PGx sample be taken pre-dose on Day 1; however, it may be obtained anytime after informed consent has been given for PGx research.
18. See Section 7.8 and collect all tumor markers applicable for the subject's primary tumor type.
19. Confirmatory assessments will occur at least 4 weeks after assessments demonstrating CR or PR. Confirmatory assessments may be conducted at a subject's next regularly scheduled visit as appropriate.
20. A blood sample for select serum safety markers (including but not limited to TNF alpha, IL-6, and tryptase) should be drawn within 24 hours of suspected infusion-related reactions.
21. For subjects who discontinue the study prior to disease progression, disease assessment must be performed either at the Follow-up visit or at the Post-Study visit prior to the start of any subsequent anticancer therapy.

Table 10 Time and Events for Part 1 PK/PD Cohorts (every week dosing schedule)

	Pre-screening	Screening	First Treatment Period (28 days)							Day 29	Continuation Phase	Follow-up ¹	Post-study ²
			First Week				Day 15	Day 22					
			Day 1	Day 2	Day 4	Day 8							
		- 14 day window ³			± 1 day window for each visit					± 2 day window for each visit	+ 7 day window		
Informed consent	X	X											
Archival tissue	X												
Tumor biopsy	X ⁴	X ⁵					X ⁶ pre-dose				X ⁷		
Skin biopsy			X pre-dose				X pre-dose						
Baseline demographics	X	X											
Medical history	X	X	X										
Concurrent Medication	Continuous										X		
Pregnancy test ⁸		X ³							X pre-dose	Every 4 weeks	X	X	
Physical examination		X	X ⁹				X		X	Every 4 weeks	X		
Height (at screening only) and weight		X	X						X	Weight: Every 4 weeks	X		
ECOG		X	X ⁹						X	Every 4 weeks	X		
Vital signs (BP, pulse rate, Temperature)		X	X ¹⁰			X	X	X	X	Every week ²²	X		
12-lead ECG		X	X ¹⁰				X		X	Every 4 weeks	X		
Hematology/Clinical Chemistry		X	X ⁹			X	X	X	X	Every week ²²	X		

	Pre-screening	Screening	First Treatment Period (28 days)						Day 29	Continuation Phase	Follow-up ¹	Post-study ²	
			First Week				Day 15	Day 22					
			Day 1	Day 2	Day 4	Day 8							
		- 14 day window ³			± 1 day window for each visit					± 2 day window for each visit	+ 7 day window		
Coagulation parameters: PT, INR, PTT		X	As Clinically Indicated										
Urinalysis		X							X	Every 4 weeks	X		
ECHO ¹¹		X							X	Every 8 weeks	X		
PK (Blood) ¹²			X	X	X	X	X	X	X	X ¹²	X	X	
Safety cytokines ²⁰			In the event of infusion reaction										
cfDNA			X pre-dose								X ⁷		
Testosterone and LH ¹³			X pre-dose						X	Every 8 weeks			
Whole blood/serum /cellular markers ¹⁴			X	X		X	X		X		X ⁷		
GSK2849330 IV infusion ¹⁵			X			X ¹⁵	X	X	X ¹⁵	Every week ¹⁵			
AE assessment			Continuous										
Serum sample for Immunogenicity			X pre-dose								X ¹⁶	X ¹⁶	
PGx Sample ¹⁷			X pre-dose										
Tumor markers ¹⁸			X							Every 8 weeks			
Disease assessment ¹⁹		X ³								Every 8 weeks	X ²¹		

1. The Follow-up visit should be approximately 28 days after the last dose of study treatment.
2. The Post-study visit should be at least 45 days or 5 half-lives (whichever is longer) after the last dose of study treatment.

3. Within 14 days prior to first dose except for pregnancy test (7 days) and Disease Assessment within 28 days prior to the first dose.
4. Separate pre-screening consent required for fresh biopsy and fresh biopsy is only collected at pre-screening if archived tissue is not available.
5. Fresh tumor biopsy is required for the PK/PD cohort; if adequate tumor biopsy is obtained during pre-screening, then this does not need to be repeated. Archival tumor tissue is not acceptable to serve as pre-treatment tumor tissue.
6. Tumor biopsy is required on Day 15 pre-dose for PK/PD cohort. Biopsy must be collected prior to administration of Day 15 dose.
7. Collected at progression. Tumor biopsy is optional and only collected from subjects with disease progression on study treatment. The tumor specimen may be collected at any time after study treatment discontinuation, but must occur prior to start of any subsequent anticancer therapy.
8. Perform only in women of childbearing potential. Serum pregnancy test should be conducted at the Screening, Follow-up, and Post-study visits. Urine pregnancy test should be conducted pre-dose on Day 29 and every 4 weeks from Day 29 in the continuation phase of the study.
9. If the screening visit was completed within 72 hours of the first dose, this assessment does not need to be repeated on Day 1.
10. Collect at pre-dose and at 1, 2, 4, and 6 hours after the start of infusion. For subjects on a weekly dosing schedule, vital signs should be conducted weekly at each dosing visit in clinic.
11. ECHO is preferred; however, if echocardiography is not available, or if reliable echocardiographic analysis of LVEF is unable to be obtained due to technical factors, a MUGA scan may be performed. Regardless, the method used at Baseline should be used for the remaining assessments in the study. Assessments should be performed more frequently than every 8 weeks if clinically indicated.
12. Blood samples for analysis of GSK2849330 concentrations will be collected Day 1: pre-dose and at 1 hour (\pm 15-minute window), 6 hours (\pm 1-hr window) and 24 hours (\pm 8-hour window) after the end of infusion. Pre-dose samples will also be collected on Day 4 (\pm 1-day window), Day 8 (\pm 1-day window) and weekly through Day 57 with additional 1-hour post-dose samples collected on Days 29 and 57. Pre-dose samples will also be collected on Day 71, Day 85 and every 12 weeks thereafter.
13. To be conducted in male subjects only.
14. Whole blood for soluble markers from plasma, serum, and/or cellular markers. Blood samples will be collected on Day 1: pre-dose and at 1 hour (\pm 15-minute window), 6 hour (\pm 1-hour window), and 24 hour (Day 2 [\pm 8-hour window]) after the end of infusion. If a subject's duration of infusion is 3 hours or longer the 6 hour time point is optional. A pre-dose blood sample should be collected on Day 8, Day 15 and Day 29 for all cohorts. An additional sample will be collected at progression.
15. For the subjects receiving a weekly dosing schedule, the study treatment dosing window is \pm 2 days The study treatment dosing window is \pm 3 days for subjects on an every 2 week dosing schedule. If dosing does not occur on the intended day, all other assessments/subsequent visits should be changed accordingly relative to when the dose was received. Subsequent cohorts may receive different dosing schedules. Use the appropriate Time and Events Table as applicable.
16. An immunogenicity sample must be collected at the Follow-up and Post-study visits.
17. It is preferred that the PGx sample be taken pre-dose on Day 1; however, it may be obtained anytime after informed consent has been given for PGx research.
18. See Section 7.8 and collect all tumor markers applicable for the subject's primary tumor type.

19. Confirmatory assessments will occur at least 4 weeks after assessments demonstrating CR or PR. Confirmatory assessments may be conducted at a subject's next regularly scheduled visit as appropriate.
20. A blood sample for select serum safety markers (including but not limited to TNF alpha, IL-6, and tryptase) should be drawn within 24 hours of suspected infusion-related reactions.
21. For subjects who discontinue the study prior to disease progression, disease assessment must be performed either at the Follow-up visit or at the Post-Study visit prior to the start of any subsequent anticancer therapy.
22. Assessments to be performed weekly while receiving weekly dosing and bi-weekly if switched to a bi-weekly dosing regimen.

Table 11 Time and Events for Part 1 PK/PD Cohorts (every 3 week dosing schedule)

	Pre-screening	Screening	First Treatment Period (21 days)				Continuation Phase	Follow-up ¹	Post-study ²	
			First Week							
			Day 1	Day 2	Day 4	Day 8				Day 22
		- 14 day window ³			± 1 day window for each visit		± 3 day window for each visit	+7 day window		
Informed consent	X	X								
Archival tissue	X									
Tumor biopsy	X ⁴	X ⁵				X ⁶ pre-dose		X ⁷		
Skin biopsy			X pre-dose			X pre-dose				
Baseline demographics	X	X								
Medical history	X	X	X							
Concurrent medication	Continuous							X		
Pregnancy test ⁸		X ³				X pre-dose	Every 3 weeks	X	X	
Physical examination		X	X ⁹			X	Every 3 weeks	X		
Height (at screening only) and weight		X	X			X	Weight: Every 3 weeks	X		
ECOG		X	X ⁹			X	Every 3 weeks	X		
Vital signs (BP, pulse rate, Temperature)		X	X ¹⁰		X	X	Every 3 weeks	X		
12-lead ECG		X	X ¹⁰			X	Every 3 weeks	X		
Hematology/Clinical Chemistry		X	X ⁹		X	X	Every 3 weeks	X		
Coagulation parameters: PT, INR, PTT		X	As Clinically Indicated							
Urinalysis		X				X	Every 3 weeks	X		
ECHO ¹¹		X				X	Every 9 weeks from day 22	X		

	Pre-screening	Screening	First Treatment Period (21 days)				Day 22	Continuation Phase	Follow-up ¹	Post-study ²	
			First Week								
			Day 1	Day 2	Day 4	Day 8					
		- 14 day window ³			± 1 day window for each visit		± 3 day window for each visit	+7 day window			
PK (Blood) ¹²			X	X	X	X	X	Day 43 and every 12 weeks	X	X	
Safety cytokines ²⁰			In the event of infusion reaction								
cfDNA			X pre-dose						X ⁷		
Testosterone and LH ¹³			X pre-dose				X	Every 9 weeks from day 22			
Whole blood/serum /cellular markers ¹⁴			X	X		X	X	Day 43	X ⁷		
GSK2849330 IV infusion ¹⁵			X				X	Every 3 weeks ¹⁵			
AE assessment			Continuous								
Serum sample for Immunogenicity			X pre-dose						X ¹⁶	X ¹⁶	
PGx Sample ¹⁷			X pre-dose								
Tumor markers ¹⁸			X					Every 9 weeks			
Disease assessment ¹⁹		X ³						Every 9 weeks	X ²¹		

1. The Follow-up visit should be approximately 28 days after the last dose of study treatment.
2. The Post-study visit should be at least 45 days or 5 half-lives (whichever is longer) after the last dose of study treatment.
3. Within 14 days prior to first dose except for pregnancy test (7 days) and disease assessment within 28 days prior to the first dose.
4. Separate pre-screening consent required for fresh biopsy and fresh biopsy is only collected at pre-screening if archived tissue is not available.
5. Fresh tumor biopsy is required for the PK/PD cohort; if adequate tumor biopsy is obtained during pre-screening, then this does not need to be repeated. Archival tumor tissue is not acceptable to serve as pre-treatment tumor tissue.
6. Tumor biopsy is required on Day 22 pre-dose for PK/PD cohort. Biopsy must be collected prior to administration of Day 22 dose.
7. Collected at progression. Tumor biopsy is optional and only required from subjects with disease progression on study treatment. The tumor specimen may be collected at any time after study treatment discontinuation, but must occur prior to start of any subsequent anticancer therapy.
8. Perform only in women of childbearing potential. Serum pregnancy test should be conducted at the Screening, Follow-up, and Post-study visits. Urine pregnancy test should be conducted pre-dose on Day 22 and every 3 weeks from Day 22 in the continuation phase of the study.
9. If the screening visit was completed within 72 hours of the first dose, this assessment does not need to be repeated on Day 1.

10. Collect at pre-dose and at 1, 2, 4, and 6 hours after the start of the first infusion.
11. ECHO is preferred; however, if echocardiography is not available, or if reliable echocardiographic analysis of LVEF is unable to be obtained due to technical factors, a MUGA scan may be performed. Regardless, the method used at Baseline should be used for the remaining assessments in the study. Assessments should be performed more frequently than every 9 weeks if clinically indicated.
12. Blood samples for analysis of GSK2849330 concentrations will be collected on Day 1: pre-dose and at 1 hour (\pm 15-minute window) and 6 hours (\pm 1-hour window) after the end of infusion. If a subject's duration of infusion is 3 hours or longer the 6-hour time point is optional. Additional PK samples will be collected at 24 hours (Day 2 [\pm 8-hr window]) and 72 hours (Day 4 [\pm 24-hour window]) after the end of infusion, and at Day 8 (\pm 1-day window and weekly through Day 57 with additional 1 hour post-dose samples collected on Days 29 and 57. Additional PK samples will also be taken every 12 weeks from the first dose within 1 year of starting treatment and if treatment continues after 1 year, samples will be collected every 24 weeks. An additional PK sample will be collected at the Post-study visit. On days of dosing sample will be drawn pre-dose.
13. To be conducted in male subjects only.
14. Whole blood for soluble markers from plasma, serum, and/or cellular marker. Blood samples will be collected on Day 1: pre-dose and at 1 hour (\pm 15-minute window), 6 hours (\pm 1-hour window), and 24 hours (Day 2 [\pm 8-hour window]) after the end of infusion. If a subject's duration of infusion is 3 hours or longer the 6-hour time point is optional. A pre-dose blood sample should be collected on Day 8, Day 22 and Day 43 for all cohorts. An additional blood sample should be collected at progression.
15. The study treatment dosing window is \pm 3 days for an every 3-week dosing schedule. If dosing does not occur on the intended day, all other assessments/subsequent visits should be changed accordingly relative to when the dose was received.
16. An immunogenicity sample will be collected at the Follow-up and Post-study visits.
17. It is preferred that the PGx sample be taken pre-dose on Day 1; however, it may be obtained anytime after informed consent has been given for PGx research.
18. See Section 7.8 and collect all tumor markers applicable for the subject's primary tumor type.
19. Confirmatory assessments will occur at least 4 weeks after assessments demonstrating CR or PR. Confirmatory assessments may be conducted at a subject's next regularly scheduled visit as appropriate.
20. A blood sample for select serum safety markers (including but not limited to TNF alpha, IL-6, and tryptase) should be drawn within 24 hours of suspected infusion-related reactions.
21. For subjects who discontinue the study prior to disease progression, disease assessment must be performed either at the Follow-up visit or at the Post-Study visit prior to the start of any subsequent anticancer therapy.

Table 12 Time and Events for Part 2 Molecularly Defined Tumor Histology Groups

	Pre-Screen	Screen	First Treatment Period (28 days)				Day 29	Continuation Phase	Follow up ¹	Post study ²
			Day 1	Day 8	Day 15	Day 22				
		-14 day window ³	± 1 day window for each visit					± 2day window for each visit	+ 7 day window	
Informed consent	X	X								
Archival tissue	X									
Tumor biopsy	X ⁴	X ⁵			X ⁶ pre-dose				X ⁷	
Baseline demographics	X	X								
Medical history	X	X	X							
Concurrent medication	Continuous									
Pregnancy test ⁸		X ³					X pre-dose	Every 4 weeks	X	X
Physical examination		X	X ⁹		X		X	Every 4 weeks	X	
Height (at screening only) and weight		X	X				X	Weight: Every 4 weeks	X	
ECOG		X	X ⁹				X	Every 4 weeks	X	
Vital signs (BP, pulse rate, Temperature)		X	X ¹⁰	X ²²	X	X ²²	X	Every week ²²	X	
12-lead ECG		X	X ¹⁰		X		X	Every 4 weeks	X	
Hematology/Clinical Chemistry		X	X ⁹	X ²²	X	X ²²	X	Every week ²²	X	
Coagulation parameters: PT, INR, PTT		X	As Clinically Indicated							
Urinalysis		X					X	Every 4 weeks	X	
ECHO ¹¹		X					X	Every 8 weeks	X	

	Pre-Screen	Screen	First Treatment Period (28 days)				Day 29	Continuation Phase	Follow up ¹	Post study ²
			Day 1	Day 8	Day 15	Day 22				
		-14 day window ³		± 1 day window for each visit				± 2day window for each visit	+ 7 day window	
PK (Blood) ¹²			X		X		X	X ¹²	X	X
Safety cytokines ²⁰			In the event of an infusion reaction							
Circulating cell free DNA (cfDNA)			X pre-dose						X ⁷	
Testosterone and LH ¹³			X pre-dose				X	Every 8 weeks		
Whole blood/serum /cellular markers ¹⁴			X	X ²²	X		X		X ⁷	
GSK2849330 IV infusion ¹⁵			X	X ²²	X	X ²²	X	Everyweek ^{15,22}		
AE assessment			Continuous							
Serum sample for Immunogenicity			X pre-dose						X ¹⁶	X ¹⁶
PGx sample			X pre-dose ¹⁷							
Tumor markers ¹⁸			X					Every 8 weeks		
Disease assessment ¹⁹		X ³						Every 8 weeks	X ²¹	

1. The Follow-up visit should be approximately 28 days after the last dose of study treatment.
2. The Post-study visit should be at least 45 days or 5 half-lives (whichever is longer) after the last dose of study treatment.
3. Within 14 days prior to first dose except for pregnancy test (7 days) and Disease Assessment within 28 days prior to the first dose.
4. Separate pre-screening consent required for fresh biopsy and fresh biopsy is only collected at pre-screening if archived tissue is not available.
5. Fresh pre- and on-treatment tumor biopsy is required; if adequate fresh biopsy tumor tissue is acquired during pre-screening, then this does not need to be repeated during the screening period. Archival tumor tissue is not acceptable to serve as pre-treatment tumor tissue.
6. Tumor biopsy is required on Day 15. Biopsy must be collected prior to study treatment administration on Day 15 dose (pre-dose).
7. Collected at progression. Tumor biopsy is optional and only collected from subjects with disease progression on study treatment. The tumor specimen may be collected at any time after study treatment discontinuation, but must occur prior to start of any subsequent anticancer therapy.

8. Perform only in women of child-bearing potential. Serum pregnancy test should be conducted at the Screening, Follow-up, and Post-study visits. Urine pregnancy test should be conducted pre-dose on Day 29 and every 4 weeks from Day 29 in the continuation phase of the study.
9. If the screening visit was completed within 72 hours of the first dose, this assessment does not need to be repeated on Day 1.
10. For vitals: collect at pre-dose and at 1, 2, 4, and 6 hours after the start of the first infusion. For ECG: collect at pre-dose and 2 hours after the start of the first infusion
11. ECHO is preferred; however, if echocardiography is not available, or if reliable echocardiographic analysis of LVEF is unable to be obtained due to technical factors, a MUGA scan may be performed. Regardless, the method used at Baseline should be used for the remaining assessments in the study. Assessments should be performed more frequently than every 8 weeks if clinically indicated.
12. Blood samples for analysis of GSK2849330 concentrations will be collected on Day 1: pre-dose and at 1 hour (\pm 15-minute window), after the end of infusion, and pre-dose on Day 15, Day 29, Day 43, Day 57, Day 71, Day 85, and every 12 weeks thereafter. If treatment continues after 1 year, samples will be collected every 24 weeks. An additional PK sample will also be taken at the Follow-up or Post-study visits. Unless stated otherwise, on days of dosing sample will be drawn pre-dose.
13. To be conducted in male subjects only.
14. Whole blood for soluble markers from plasma, serum, and/or cellular markers. Blood samples will be collected on Day 1: pre-dose and at 1 hour (\pm 15-minute window) and 6 hours (\pm 1-hour window) after the end of infusion. If a subject's duration of infusion is 3 hours or longer, the 6-hour time point is optional. A pre-dose blood sample should be collected on Day 8, Day 15 and Day 29 for all cohorts. An additional sample will also be collected at progression.
15. For the subjects receiving a weekly dosing schedule, the study treatment dosing window is \pm 2 days. The study treatment dosing window for all other dosing schedules (e.g., an every 2-week or every 3-week dosing schedule) is \pm 3 days. If dosing does not occur on the intended day, all other assessments/subsequent visits should be changed accordingly relative to when the dose was received.
16. An immunogenicity sample must be collected at the Follow-up and Post-study visits.
17. It is preferred that the PGx sample be taken pre-dose on Day 1; however, it may be obtained anytime after informed consent has been given for PGx research.
18. See Section 7.8 and collect all tumor markers applicable for the subject's primary tumor type.
19. Confirmatory assessments will occur at least 4 weeks after assessments demonstrating CR or PR. Confirmatory assessments may be conducted at a subject's next regularly scheduled visit as appropriate.
20. A blood sample for select serum safety markers (including but not limited to TNF alpha, IL-6, and tryptase) should be drawn within 24 hours of suspected infusion-related reactions.
21. For subjects who discontinue the study prior to disease progression, disease assessment must be performed either at the Follow-up visit or at the Post-Study visit prior to the start of any subsequent anticancer therapy.
22. Assessments to be performed weekly while receiving weekly dosing and bi-weekly if switched to a bi-weekly dosing regimen.

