5.2.4. Inclusion Criteria for Part 2 ONLY

As listed above for Part 1, with the exception of criterion 3 which should be replaced with the following criterion 9 and the addition of criteria 10 and 11.

9. For Group 1: subjects with previously treated, unresectable stage III or IV melanoma with documented HER3 expression (3+) on the cell surface of the invasive component of the tumor using an analytically validated IHC assay by central laboratory.
- Subjects must have no more than 3 prior lines of systemic regimens and have disease progression on or after last prior treatment (based on RECIST v1.1).
 - Subjects with BRAF V600 mutations who already received or were intolerant of prior BRAF inhibitor therapy may be included.
 - Subjects may be included if they had prior immune therapy, or were intolerant of prior immune therapy.

For Group 2: Subjects with previously treated, unresectable stage III or IV gastric or gastroesophageal junction (GEJ) adenocarcinoma with documented HER3 expression (3+) on the cell surface of the invasive component of the tumor using an analytically validated IHC assay by central laboratory.

- Subjects must have no more than 3 prior lines of systemic regimens and have disease progression on or after last prior treatment (based on RECIST v1.1).
- Subjects with HER2 positive disease may be included if they had prior anti-HER2 therapy or were intolerant of prior anti-HER2 therapy.

For Group 3: Subjects with previously treated, unresectable stage III or IV cancers of the head and neck with documented HER3 expression on the cell surface of the tumor ($\geq 1+$) and NRG1 expression using analytically validated assays by central laboratory.

- Subjects must have no more than 3 prior lines of systemic therapy and have disease progression on or after last prior treatment (based on RECIST v1.1).
- Subjects with locoregional recurrences amenable to definite surgery or additional radiation are excluded.

For Group 4: Subjects with previously treated, unresectable stage III or IV NSCLC with documented HER3 expression on the cell surface of the tumor ($\geq 1+$) and NRG1 expression using analytically validated assays by central laboratory.

- Subjects must have no more than 3 prior lines of systemic regimens and have disease progression on or after last prior treatment (based on RECIST v1.1).
- Subjects with anaplastic lymphoma kinase (ALK) translocation who already received or were intolerant of prior anti-ALK therapy may be included.

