2. The Post-study visit should be at least 45 days or 5 half-lives (whichever is longer) after the last dose of study treatment.
3. Within 14 days prior to first dose except for pregnancy test (7 days) and Disease Assessment within 28 days prior to the first dose.
4. Separate pre-screening consent required for fresh biopsy and fresh biopsy is only collected at pre-screening if archived tissue is not available.
5. Fresh tumor biopsy is required for the PK/PD cohort; if adequate tumor biopsy is obtained during pre-screening, then this does not need to be repeated. Archival tumor tissue is not acceptable to serve as pre-treatment tumor tissue.
6. Tumor biopsy is required on Day 15 pre-dose for PK/PD cohort. Biopsy must be collected prior to administration of Day 15 dose.

7. Collected at progression. Tumor biopsy is optional and only collected from subjects with disease progression on study treatment. The tumor specimen may be collected at any time after study treatment discontinuation, but must occur prior to start of any subsequent anticancer therapy.
8. Perform only in women of child-bearing potential. Serum pregnancy test should be conducted at the Screening, Follow-up, and Post-study visits. Urine pregnancy test should be conducted pre-dose on Day 29 and every 4 weeks from Day 29 in the continuation phase of the study.
9. If the screening visit was completed within 72 hours of the first dose, this assessment does not need to be repeated on Day 1.
10. Collect at pre-dose and at 1, 2, 4, and 6 hours after the start of the first infusion
11. ECHO is preferred; however, if echocardiography is not available, or if reliable echocardiographic analysis of LVEF is unable to be obtained due to technical factors, a MUGA scan may be performed. Regardless, the method used at Baseline should be used for the remaining assessments in the study. Assessments should be performed more frequently than every 8 weeks if clinically indicated.
12. Blood samples for analysis of GSK2849330 concentrations will be collected Day 1: pre-dose and at 1 hour (\pm 15-minute window), 6 hours (\pm 1-hour window) and 24 hours (\pm 8-hour window) after the end of infusion. Pre-dose samples will also be collected on Day 4 (\pm 1-day window), Day 8 (\pm 1-day window) and weekly through Day 57 with additional 1-hour post-dose samples collected on Days 29 and 57. Pre-dose samples will also be collected on Day 71, Day 85 and every 12 weeks thereafter.
13. To be conducted in male subjects only.

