13.5.2. Other Comparisons of Interest

In Part 1, PK parameters including, but not limited to, AUC(0-t), AUC(0-τ), AUC(0-∞), C_{max}, t_{max}, and MRT of GSK2849330 will be descriptively compared between dose

levels in tabular or graphic formats. In Part 2, other safety, PK and clinical activity data than the primary endpoints will also be evaluated and compared between different treatment groups.

- PK: PK parameters including, but not limited to, AUC(0-t), AUC(0- τ), AUC(0- ∞), Cmax, tmax, and MRT of GSK2849330 will be descriptively compared between dose levels in tabular or graphic formats.
- PD biomarker: Changes from baseline in PD markers, the markers of inflammatory response activation from blood and markers in skin and tumor biopsies will be evaluated and summarized for each dose cohort or group.
- Clinical anti-cancer activity: The number of CRs, PRs, stable diseases (SDs) and PDs for each dose cohort or group will be listed using RECIST, irRC, and mRECIST and summarized if appropriate.

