# 14. PHARMACODYNAMIC AND BIOMARKERS ANALYSES

# 14.1. Pharmacodynamic Analyses

Pre-treatment and on-treatment biopsy tissues (tumor and normal skin) will be analyzed for markers of the HER3 pathway such as HER3 and including biomarkers indicative of pathway activation and proliferation (pHER3, Ki67) using IHC as the method to determine protein expression levels. Markers related to the other mechanisms of action attributed GSK2849330 such as ADCC and CDC may be analyzed.

Serum HER3 (also known as 'soluble HER3') pre and on-treatment analyses will be performed. Descriptive summary (mean, SD, median, minimum, maximum) of absolute test value will be reported by dose group. The summary of change from baseline serum HER3 will also be provided. The baseline of HER3 data is defined as the test value measured at Day 1 Pre-dose. The individual serum HER3 concentration over time data for will be plotted. Box plot figures will be generated as a function of the dose administered. Listing of the serum HER3 data will be provided.

Data permitting, exploratory population PD analyses of other peripheral blood markers will be provided.

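### When the biopsy that met the HER3 entry cut-off is also the pre-treatment sample, tumour total HER3 is expected to read lower on treatment even with an inert drug

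*Protocol*

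**What the plan says.** **Entry cut-offs.** Under protocol 5.2.4, Group 1 takes "unresectable stage III or IV melanoma with documented HER3 expression (3+) on the cell surface of the invasive component of the tumor" and Group 2 takes "gastroesophageal junction (GEJ) adenocarcinoma with documented HER3 expression (3+) on the cell surface". Groups 3 and 4 need only 1+ or more, plus NRG1; the Group 3 wording is "cancers of the head and neck with documented HER3 expression on the cell surface of the tumor". Part 1 (5.2.3, criterion 3) accepts 2+ or 3+.

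**Which tissue is tested.** Section 7.6.1.1 asks for a fresh biopsy for the eligibility test when no archival tissue exists. Footnote 4 of Table 12 confines fresh pre-screening biopsies to that case.

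**Which tissue is the baseline.** Footnote 5 of Table 12 adds that "if adequate fresh biopsy tumor tissue is acquired during pre-screening, then this does not need to be repeated during the screening period". Footnote 5 of Tables 9 to 11 has the same rule for the Part 1 PK/PD cohorts: "if adequate tumor biopsy is obtained during pre-screening, then this does not need to be repeated". Both versions bar archival tissue as the pre-treatment sample.

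**The comparison.** The on-treatment biopsy is taken before dosing on Day 15 (Day 22 in Table 11). Total and phospho-HER3 in tumour are secondary endpoints in both parts (2.1, 2.2). Protocol 13.5.2 states "Changes from baseline in PD markers, the markers of inflammatory response activation from blood and markers in skin and tumor biopsies will be evaluated" and summarised by dose cohort or group. SAP 14.1 measures the tissue markers "using IHC as the method to determine protein expression levels". The PD Population in SAP 6 requires an evaluable pair and does not consider where the baseline came from. Every enrolled subject receives GSK2849330 (3.7.1), so there is no control.

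**The concern.** A baseline that had to be high for the subject to enter is partly high by chance: where the needle went, and how the slide stained and was read. The next biopsy does not share that chance, so on average it reads lower. With no control arm and no second pre-treatment reading, the summary cannot separate this fall from a drug effect.

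The plan creates two kinds of baseline. A subject selected on archival tissue has a later fresh baseline that played no part in selection. A subject without archival tissue may have the selection sample itself as baseline. Only the second kind is biased, and always in the direction that looks like pharmacology. What is at stake is the total-HER3 part of the target-engagement summary. The distortion differs between cohorts according to how many subjects lacked archival tissue.

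**Working it through.** The plan states no figure for paired change, biopsy-to-biopsy agreement or 3+ prevalence, so there is nothing to reproduce. The direction follows from the design. The size needs assumptions.

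**Model, inert drug.** X is the selection reading and Y the on-treatment reading, each with SD 1 and correlation r. A subject enters if X > c, where P(X > c) = p, the 3+ prevalence.

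- Reused baseline: expected change = -(1 - r) × φ(c)/p. This is negative for every r below 1.
- Independent baseline B: B and Y are exchangeable given X > c. The expected change is 0, and false falls and rises balance.
- Chance that a subject who entered at 3+ reads below 3+ on treatment = 1 - P(X > c and Y > c)/p.

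**Central case, p = 0.20 and r = 0.8.** c = 0.842, φ(c) = 0.280 and φ(c)/p = 1.40. The mean fall is 0.2 × 1.40 = 0.28 SD, and the chance of reading below 3+ is 0.355.

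**Assumed range.** Each cell gives the chance of reading below 3+, then the mean fall in SD.

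| p | r = 0.6 | r = 0.7 | r = 0.8 | r = 0.9 |
|---|---|---|---|---|
| 0.10 | 0.61; 0.70 | 0.53; 0.53 | 0.44; 0.35 | 0.31; 0.18 |
| 0.20 | 0.50; 0.56 | 0.44; 0.42 | 0.36; 0.28 | 0.25; 0.14 |
| 0.30 | 0.42; 0.46 | 0.37; 0.35 | 0.30; 0.23 | 0.21; 0.12 |

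**Group level.** Reused 3+ baselines cannot produce offsetting rises on the category score, and independent pairs contribute no net change. The net false decrease is therefore the reuse share times the chance above. The reuse share is assumed to be 15% to 40%.

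- Central chance: 0.15 × 0.355 = 5.3 points; 0.40 × 0.355 = 14.2 points.
- Extremes: 0.15 × 0.21 = about 3 points; 0.40 × 0.61 = about 24 points.
- Central mean shift: 0.15 × 0.28 = 0.04 SD; 0.40 × 0.28 = 0.11 SD.

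**Where selection is weaker.** As an illustration for Part 1, take half of tumours at 2+ or 3+ and r = 0.8. Then φ(0)/0.5 = 0.798, and the mean fall in a reused pair is 0.2 × 0.798 = 0.16 SD. Groups 3 and 4, at 1+ or more, are also selected less strongly than the 3+ groups.

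**The case against.** The strongest reply is that little rests on this. No test is planned on tumour HER3. SAP 19.1.4 gives summary tables for serum HER3 and CD markers only, and tumour markers appear only in the general biomarker listing, item 12.5. The affected share may be small. The central shift of 0.04 to 0.11 SD is below the standard error of a group mean: √(2 × 0.2) = 0.63 SD per pair, so 0.63/√12 = 0.18 SD with 12 pairs and 0.63/√30 = 0.12 SD with 30. Footnote 5 also reuses tissue and not a score. If the pairs are re-stained, the assay part of the error goes. If they are read on a continuous scale, the ceiling at 3+ goes.

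Much of this stands, and it limits the point to a bias in a descriptive summary. It does not remove it. Protocol 13.5.2 still promises a summary of change by cohort or group, re-staining leaves the sampling part of the error, and SAP 14.1 states neither the scale nor the reading procedure. More pairs would shrink the standard error but not the bias.

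A reader might also infer that the 3+ groups distort the choice of Part 2 regimen. The documents do not support that: Part 2 opens after the regimen is identified (3.4), so only Part 1 pairs could bear on it. There a 2+ baseline can rise as well as fall, and the choice rests on safety, PK, PD and the N-CRM output together (3.3).

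**Conclusion.** The point holds for subjects whose eligibility biopsy is also their pre-treatment sample. The direction needs only that two biopsies of one untreated tumour correlate below 1. The effect is strongest in Groups 1 and 2, where a 3+ category score can only stay or fall, since 3+ is the highest score the documents name. It is weaker in Part 1 and in Groups 3 and 4. In a 3+ group the net false decrease is about 3 to 24 percentage points over the full assumed ranges, or 5 to 14 if only the reuse share varies around the central case. Prevalence, correlation and reuse share are all assumed.

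Three stronger readings are not supported:

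- That total HER3 falls artificially in all subjects. Those selected on archival tissue are unaffected.
- That the plan defines a fall in total HER3 as its evidence of target engagement. Total and phospho-HER3 are listed against that objective, but no direction, threshold or decision rule is given.
- That an error rate is inflated. No test is planned.

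**What to change.** In protocol 13.5.2, SAP 14.1 and the biomarker listing (SAP 19.1.4, item 12.5), flag each pair by whether its baseline biopsy was also the eligibility sample. Present the change in total HER3 separately for independent-baseline and reused-baseline pairs. Rest any target-engagement statement on total HER3 mainly on the independent pairs. Read it alongside phospho-HER3, which is already a co-listed endpoint and was not a selection variable, so it is affected only through its correlation with total HER3. State the IHC scale used for the paired reading.

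This needs wording and one flag, and no further biopsy. Because it changes only reporting, the early stopping noted in SAP 11 does not prevent it. The cost is fewer pairs in each summary, which matters most in the PK/PD cohorts of up to three subjects per dose level; there, a flagged listing may be all that is practical.
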